623 measurement of HbA1c. While part of routine diabetes care, this can be painful and
624 distressing to some patients. There is a very slight risk of infection and bruising at the
625 site of the fingerstick.

626

627 Hypoglycemia

628 As with any person having insulin-dependent diabetes, there is always a risk of having a
629 low blood sugar (hypoglycemia). The frequency of nocturnal hypoglycemia should be
630 no more than it would be as part of daily living with diabetes. Symptoms of
631 hypoglycemia can include sweating, jitteriness, and not feeling well. Just as at home,
632 there is the possibility of loss of consciousness or seizures (convulsions) and that for a
633 few days you may not be as aware of symptoms of low blood sugar. Even if severe low
634 blood sugar does occur, it almost always goes away quickly with treatment to raise the
635 blood sugar.

636

637 Hyperglycemia

638 Since we are asking subjects to wear an insulin infusion set for 10 days, there will be a
639 higher risk for hyperglycemia occurring than would occur if infusion sets were changed
640 every three days. A delayed change in an infusion set could therefore cause an
641 additional episode of hyperglycemia with extended infusion set wear. Since subjects
642 will be performing frequent monitoring of their blood glucose and monitoring blood
643 ketone levels in the event of hyperglycemia, these events should be of limited duration
644 and ketosis should be detected early and easily treated.

645

646 **Protection against Risks and Treatment of Side Effects**

647 Subjects will be given descriptions of possible local side effects with insulin infusion sets
648 or sensor insertion sets. They will be told to contact the study staff if they see any signs
649 of a skin reaction. Based on the severity of local skin reaction, topical anti-inflammatory
650 medications can be used (such as topical steroids).

651

652 Subjects will be instructed on the signs and symptoms of hypoglycemia and
653 hyperglycemia, and appropriate management to correct these states. They will be
654 instructed in the use of glucagon emergency kit for reversal of severe hypoglycemia.
655 For hyperglycemia, they will be instructed to ensure the insulin pump is appropriately

656 functioning, and there are no obstructions in the insulin infusion set. They will also be
657 instructed to check serum ketones. If hyperglycemia persists, they will be instructed to
658 use subcutaneous insulin injections, and change to a new insulin infusion set.

659

660 All subjects that wish to have a topical anesthetic applied prior to insulin infusion set and
661 Continuous Glucose Monitoring (CGM) sensor insertion will have this option available to
662 them.

663

664 **Other Risks**

665 Some subjects may develop skin irritation or allergic reactions to the adhesives used to
666 secure the CGM sensor or infusion set. If these reactions occur, different adhesives or
667 "under-taping" (such as with IV 3000, Tegaderm, etc.) will be tried, sites will be rotated
668 frequently, and a mild topical steroid cream or other medication may be required.

669

670 Whenever the skin is broken there is the possibility of an infection. The CGM sensor
671 and insulin infusion set sites are inserted under the skin. It is possible that any part that
672 is inserted under the skin may cause an infection. These occur infrequently, but, if an
673 infection was to occur, oral and/or topical antibiotics can be used, and they generally
674 respond quickly to a short course of oral antibiotics such as cefaclor. The risk of skin
675 problems could be greater if a sensor or infusion set is used for extended periods of
676 time. Therefore participants will be carefully instructed about daily inspection of their
677 sensor and infusion set sites.

678

679 Data downloaded from the CGM sensor, insulin pump, and the home glucose and
680 ketone meters will be collected for the study as measures of diabetes self-management
681 behaviors. Some people may be uncomfortable with the researchers having such
682 detailed information about their daily diabetes habits.

683 **CHAPTER 5: Miscellaneous Considerations**

684

685 **Potential Benefits**

686 Continuous Glucose Monitoring (CGM) data will provide each subject individualized
687 information about their glucose response to variables such as meals and exercise that
688 may help in their management of diabetes.

689

690 The ability to wear an infusion set for extended periods may help decrease local skin
691 reactions from the frequent insertion and removal of infusion sets which results in
692 removal of portions of the top layer of the epidermis which may lead to a higher risk of
693 infections if a new infusion set or sensor is inserted into this area before the epidermis is
694 completely healed.

695

696 If there is less unexplained hyperglycemia and fewer episodes of ketosis with prolonged
697 infusion set wear as a result of the Lantern infusion set, this would be a significant
698 benefit to all people using insulin infusion pumps.

699

700 If the Lantern infusion set could extend the use of a subcutaneous infusion sets to 7-10
701 days, this would allow of the future development of a combination infusion set and
702 continuous glucose sensor. Such a platform would play an integral role in the
703 development of a simplified closed-loop artificial pancreas system.

704

705 **Subject Compensation**

706 Subjects will be compensated \$50 for each outpatient study visit and \$20 for each entry
707 into REDCap or contact with a study investigator. Maximum payment of \$280 for all
708 study visits in Part 1 and \$530 for participating in Part 2. Compensation of partial
709 participation will be prorated.

710

711 **Subject Withdrawal**

712 Participation in the study is voluntary, and a subject may withdraw at any time. The
713 investigator may withdraw a subject who is not complying with the protocol. For subjects
714 who withdraw, their data will be used up until the time of withdrawal.

715

716 **Subject Discontinuation Criteria**

717 Subjects who become pregnant will be discontinued from the study. The investigator
718 may withdraw a subject who is not complying with the protocol. Withdrawal of a subject
719 will be considered for the following reasons:

720

721

722

723

1. Failure to monitor their sensor and infusion sites on a daily basis
2. Developing >1.0 mmol/L ketones on 2 or more occasions and failing to change
their infusion set or a single episode of diabetic ketoacidosis due to an infusion
site failure

724

725 For subjects who withdraw or who are withdrawn, their data will be used for analysis
726 purposes up until the time of withdrawal.

728 **Confidentiality**
729 For security and confidentiality purposes, subjects will be assigned an identifier that will
730 be used instead of their name. De-identified subject information may be provided to the
731 funder.

732
733 **Level of Risk**

734 This research proposal in children is consistent with United States Department of Health
735 and Human Services, Protection of Human Subjects, Subpart D, Section 46.404
736 (Research not involving more than minimal risk).

737
738 **Planned Duration of the Entire Study**
739

Planned duration of the entire study will be 12 months.

740 **CHAPTER 6: Statistical Considerations**

741

742 **Part 1**

743 Before beginning a larger cross-over study we would perform this pilot study to
744 determine the maximum length of Lantern infusion set wear when 80% are still
745 functional if failure was not due the infusion set being accidentally pulled out. This study
746 is not statistically powered.

747

748 **Part 2**

749 Primary Outcome

750 Our primary outcome will be time to failure of each infusion set. We have reviewed 353
751 weeks of infusion set wear from prior studies [19-20, unpublished data] and subjects
752 who wear the control set have an average length of wear of 5.1 days with a standard
753 deviation of 1.7 days and intra-subject correlation of 0.69. For a meaningful clinical
754 benefit, the subjects who wear the treatment set should extend wear by at least 1 day to
755 an average length of wear of 6.1 days. A sample size of 40 subjects will provide 95%
756 power to detect a difference of 1 day in the average length of wear in a two-sided test
757 with an alpha level of 0.05. A minimum of 25 subjects must be recruited for 80% power.

758

759 Exploratory Outcomes

760 Other outcomes will include – BMI, cause of infusion set failure, measurements of
761 erythema and induration, pump insulin delivery data, glucometer readings, ketone meter
762 data, average daily CGM blood glucose, DSAT/DDS score and infusion set
763 questionnaire.

764

765 We will summarize the other secondary measures using means, standard deviation,
766 medians, ranges, proportions and 95% confidence interval, as appropriate. We will also
767 explore the relationship between BMI, DSAT/DDS score and the time to failure primary
768 outcome. Finally, we will test if there is a significant change in the DSAT/DDS score
769 following participation in the clinical trial.

770 **CHAPTER 7: References**

1. The Diabetes Control and Complications Trial Research Group. "The effect of intensive treatment of diabetes on the development and progression of long-term complications in insulin-dependent diabetes mellitus. The Diabetes Control and Complications Trial Research Group." *N Engl J Med.* 1993 Sep 30;329(14):977-86.
2. Diabetes Control and Complications Trial/Epidemiology of Diabetes Interventions and Complications (DCCT/EDIC) Study Research Group. "Intensive diabetes treatment and cardiovascular disease in patients with type 1 diabetes." *N Engl J Med.* 2005 Dec 22;353(25):2643-53.

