218 cause of set failure. If a set is accidentally pulled out, it can be replaced by the subject.
219 Subjects will either complete a daily online questionnaire or they will be contacted daily
220 by research staff to determine if a set has failed, the cause of failure, and to record
221 measured erythema and edema at a failed infusion site. Failures are based on:
222

- 223 1. Presence of serum ketones with hyperglycemia
- 224 2. Unexplained hyperglycemia
3. Signs of infection at the infusion site

225 4. Pump occlusion alarm
226 5. Adhesive failure

227
228 Since infusion set failures will occur after variable lengths of wear, regularly scheduled
229 visits are unlikely to capture the day of an infusion set failure. Instead the subject will be
230 taught how to insert the set, measure erythema and induration with a ruler marked in
231 millimeters and to take a picture of the infusion site. Subjects will be instructed to text
232 the study team when they remove their infusion set and to send a picture of the infusion
233 site and measurements. If there is any evidence of an infection (≥ 10 mm of erythema or
234 induration), they will be asked to come in that day for an unscheduled visit.

[figure not shown]
235
236 Part 2: Extended Wear Randomized Controlled Crossover Study

237 This will be a masked, randomized controlled crossover study at Stanford University
238 (**Figure 4**). The study is intended for registration purposes and to support a 510(k)
239 submission. The planned duration of wear and visit schedule will be determined by the
240 results of Part 1. Participants, age 15 and over, will be randomized to wear the masked
241 investigational or control infusion set first. The control set is the Mio (used with
242 Medtronic pumps) or Inset II (used with other pump models) which are the precursors to
243 the Convatec Lantern and do not contain slits. Each participant will wear both the
244 investigational and control infusion set. Subjects will act as their own control.

245
246 At home subjects will examine their infusion site when they are changing an infusion set
247 and assess for signs of bleeding, local tissue reaction or infection. They will record
248 redness, induration, and bruising in mm, and call one of the investigators if there is
249 more than 10 mm of erythema or induration. They will be given a ruler for making these
250 measurements. If there is more than 3 mm of induration or redness they will be asked to

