405 ketones using a blood ketone meter if there is unexplained hyperglycemia. Unexplained
406 hyperglycemia refers to high glucose levels outside of the usual times they may occur,
407 such as in the initial few hours following a meal. If the CGM stops functioning during the
408 study, the subjects will insert a new sensor which will be provided to them. If there is an
409 accidental removal of an infusion set the participant will have access to a replacement
410 which he or she will be taught to place.

411

412 *Determination of an infusion set failure:*

413 They will be instructed to replace their infusion set, in the following situations.

414 1. The presence of serum ketones >0.6 mmol/L with meter glucose >250 mg/dL, in
415 the absence of illness, vigorous fat burning exercise, starvation or alcohol.
416 2. Unexplained hyperglycemia, >250mg/dL, outside anticipated periods of
417 carbohydrate consumption, illness, missed insulin doses and menstruation. This
418 hyperglycemia cannot be reduced with appropriate correction doses of insulin
419 (such as a decrease of at least 50mg/dL in 1 hour following a correction dose).
420 3. Signs of infection at the infusion site including pain, erythema or induration >10
421 mm in diameter.
422 4. Pump occlusion alarm
423 5. Adhesive failure (only the adhesive on the infusion set will be used)

424
425 *Recording of infusion site information:* At home they will examine their infusion site each
426 day for signs of redness and/or induration. If they detect redness or induration they will
427 record them in mm and send a text to study staff. At the time an infusion set is removed
428 they will record redness and induration in millimeters, and call one of the investigators if
429 there is more than 10 millimeters of erythema or induration. They will be given a ruler
430 for making these measurements. Subjects will record the time and date that infusion
431 sets or sensors are removed, and document why they removed the set and take a
432 picture of the infusion site after the infusion set is removed if there is >3 mm of
433 erythema. The picture and infusion site measurements will be sent via text or e-mail to
434 study staff, if there is not concern about infection.

435
436 **Final Visit**

437 Within fourteen days after the study infusion set was inserted, subjects will have their
438 final study visit. At the final study visit all infusion sets, glucose sensors, study pumps

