474 labeling. While the G6 system is FDA approved for non-adjunctive use without
475 calibration, we will ask patients to confirm blood glucose with glucometer prior to
476 removing an infusion set. Subjects will be instructed to check blood ketones using a
477 blood ketone meter if there is unexplained hyperglycemia. Unexplained hyperglycemia
478 refers to high glucose levels outside of the usual times they may occur, such as in the
479 initial few hours following a meal. If the CGM stops functioning during the study, the
480 subjects will insert a new sensor which will be provided to them. If there is an
481 accidental removal of an infusion set the participant will have access to a replacement
482 which he or she will be taught to place.
483

484 *Determination of an infusion set failure:*

485 They will be instructed to replace the infusion set, in the following situations.

- 486 1. The presence of serum ketones >0.6 mmol/L with meter glucose >250 mg/dL, in
487 the absence of illness, vigorous fat burning exercise, starvation or alcohol.
- 488 2. Unexplained hyperglycemia, >250 mg/dL, outside anticipated periods of
489 carbohydrate consumption, illness, missed insulin doses and menstruation. This
490 hyperglycemia cannot be reduced with appropriate correction doses of insulin
491 (such as a decrease of at least 50 mg/dL in 1 hour following a correction dose).
- 492 3. Signs of infection at the infusion site including pain, erythema or induration >10
493 mm in diameter.
- 494 4. Pump occlusion alarm
- 495 5. Adhesive failure (only the adhesive on the infusion set will be used)

496
497 *Recording of infusion site information:* At home they will exam their infusion site each
498 day for signs of redness and/or induration. If they detect redness or induration they will
499 record them in mm and send a text to study staff. At the time an infusion set is removed
500 they will record redness and induration in millimeters, and call one of the investigators if
501 there is more than 10 millimeters of erythema or induration. They will be given a ruler
502 for making these measurements. Subjects will record the time and date that infusion
503 sets or sensors are removed, and document why they removed the set and take a
504 picture of the infusion site after the infusion set is removed if there is ≥ 3 mm of

505 induration or erythema. The picture and infusion site measurements will be sent via text

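### Do the differing 10 mm wordings and the two adhesive statements leave the set-failure outcome ambiguous?

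*Combined protocol and SAP*

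**What the plan says.** **Site reaction.**

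- Chapter 1, Protocol Synopsis, Part 1: subjects text the team when they take the set out and send a picture and measurements. The next sentence begins "If there is any evidence of an infection (≥ 10 mm of erythema or" induration, and continues "they will be asked to come in that day for an unscheduled visit".
- Chapter 3, Part 1, Determination of an infusion set failure, criterion 3: "Signs of infection at the infusion site including pain, erythema or induration >10" mm in diameter.
- Chapter 3, Part 1, Recording of infusion site information: at removal the subject calls an investigator if "there is more than 10 millimeters of erythema or induration".
- Part 2: the synopsis sets the call at "more than 10 mm of erythema or induration", and Chapter 3 repeats the Part 1 failure criterion and call rule.

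**Adhesive.**

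- Chapter 3, criterion 5, both parts: "Adhesive failure (only the adhesive on the infusion set will be used", with no exception stated.
- Chapter 4, Other Risks, on skin reactions to the adhesives that "secure the CGM sensor or infusion set. If these reactions occur, different adhesives or" under-taping will be tried, along with frequent site rotation and topical treatment.

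The failure lists in the synopsis name signs of infection and adhesive failure without a size or a taping condition.

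**The concern.** Time to set failure is the Part 2 primary outcome. Part 1 uses the failure count to fix the Part 2 wear length, as the longest wear at which 80% of sets still function. A rule stated in two ways could therefore lead to the same site being counted in two ways.

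The ruler is marked in millimetres, so a reading of exactly 10 mm can occur. On size alone it is evidence of infection in the Part 1 synopsis, but in Chapter 3 it is neither a failure nor a reason to call.

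Extra tape changes the chance that a set comes loose. In a crossover, tape used in one period only would put a subject's two sets under different conditions.

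The scale also looks worrying at first. Chapter 1, Etiology of Infusion Set Failures, attributes 5-10% of failures to erythema or induration and 6-12% to loss of adhesion. With 24 sets in Part 1, one set is 4.2 percentage points against the 80% rule.

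**Working it through.** The plan gives no figure on this point to reproduce. The check compares the passages and then bounds the numbers.

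**1. Is there a second failure threshold?** The documents attach a size to set failure twice, in criterion 3 of Chapter 3 for Part 1 and for Part 2. Both say more than 10 mm. The synopsis wording "any evidence of an infection (≥ 10 mm of erythema or" induration governs an unscheduled visit. It follows the instruction about removing the set and sending measurements, so in that sequence the set is already out. It does not say that a set still in place has failed.

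**2. Would a 10 mm reading be missed?** Chapter 3, Part 1 has subjects inspect the site daily, record any redness or induration in millimetres and text staff. Daily contact by REDCap, text or telephone also collects the measurement. Staff hold the reading under either wording.

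**3. Does the mismatch reach Part 2?** Not directly. The Part 2 synopsis and Chapter 3 both use more than 10 mm. The only route is the wear length chosen from Part 1.

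**4. What do the alarming figures measure?**

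- 5% + 6% = 11% and 10% + 12% = 22%. These are shares of all failures from the two causes, not of failures whose classification is in doubt.
- 1/24 = 4.2 points, 20/24 = 83.3% and 19/24 = 79.2%. One set could cross the 80% line, but only if a set were reclassified, and step 1 finds no second failure threshold to do that.
- If every Part 1 set failed, erythema or induration would account for 24 × 5-10% = 1.2 to 2.4 sets. Those at exactly 10 mm are a fraction of that.

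**5. Which sets can the taping text reach?** Known tape allergy is an exclusion. After a failure beyond 24 hours the subject goes back to the usual set, so much of the Chapter 4 text can apply to sensors and usual sets. Under-tape goes beneath the adhesive and so before insertion. That leaves mainly a replacement study set, or the second Part 2 set after a reaction to the first.

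**6. How large could that be in Part 2?** The documents give no taping rate. Assume that 5-10% of the 40 second sets are taped (borrowing the erythema/induration share), that every set fails, and that 6-12% of failures are adhesive.

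- Taped second sets: 40 × 5-10% = 2 to 4.
- Adhesive failures expected among them without tape: 2 × 6% = 0.12 to 4 × 12% = 0.48.
- Ceiling if all 40 second sets were taped: 40 × 6-12% = 2.4 to 4.8.
- Leverage of one set: if tape added a whole average wear of 5.1 days to one set, the mean within-subject difference would move by 5.1/40 = 0.13 day, against the 1-day difference the trial is sized to detect.

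The order of sets is randomized, so the second set is sometimes the Lantern and sometimes the control. Taping that follows a first-set reaction does not systematically favour either unless reaction rates differ between them.

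**The case for a change.** The strongest case for acting is that both contradictions stand in the current text and cost only a few words to remove. The synopsis failure list says signs of infection with no size, and the only size given for infection in that Part 1 synopsis is 10 mm or more, so a reader of the synopsis alone could carry it into the failure count. Chapter 4 names the infusion set, so it cannot be read as covering sensors only, and nothing says how a taped study set counts. Part 2 is meant to support a 510(k) submission, where consistent definitions matter. If one set type irritates skin more, taping would not be balanced between them.

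The textual facts stand. The inference to the failure count is weak, because Chapter 3 has a section devoted to determining failure and supplies the size that the synopsis omits. The taping gap is genuine but narrow. An analyst can apply criterion 5 as written and note any recorded tape use.

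The one proposal that would alter the analysis is to censor a taped set for adhesive failure from the time of taping. It is not a clear gain. Taping follows a skin reaction, so the censoring may be informative, and under-tape placed before insertion would mean censoring at time zero.

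**Conclusion.** The concern is right about the wording but shows no effect on a result. The size threshold for set failure is the same wherever one is given. The 10 mm mismatch is confined to the Part 1 visit and call rules at one exact reading, which staff receive in any case. The adhesive mismatch concerns a few sets at most: 0.12 to 0.48 expected adhesive failures among taped second sets under the stated assumption, and 2.4 to 4.8 if every second set were taped. The 11-22% and 4.2-point figures do not measure either effect.

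This rests on the required texts and daily contacts taking place, on taping being uncommon, and on reaction rates not differing greatly between the two sets. Only the last two bear on the primary comparison.

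The paired passages do contradict each other on how a site is handled. The investigators must reconcile them, including whether the Chapter 4 taping text covers study sets. That is editorial alignment, and the sample size, the primary outcome and its analysis stay as they are.
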